7.3.5. Heat Pain Threshold Test

Heat pain threshold tests will be conducted at the times indicated in the Schedule of Assessments ([Appendix 6](#)).

A computer-controlled thermal sensory analyzer device will be used to measure the heat pain threshold and tolerance level of the subjects. The heat pain assessments will be conducted on the subject's thigh.

Heat Pain Threshold:

For heat pain threshold measurements, the thermode will be placed directly on the skin of the right thigh, within an area selected before the start of the experiment and defined by surgical marking. The thermode will have a baseline temperature of 32°C, and will be programmed to gradually increase at a rate of 1.0°C per second. The subject will be given a controller in their dominant hand, to indicate when the heat pain threshold (first sensation of heat pain) is reached by pushing a button. At that time, the test will be stopped and the temperature returned to baseline within 1 second. This process will be repeated a further 2 times, with an interval of at least 1 minute between measurements (from start to start). The computer will record the average value of 3 experiments.

Heat Pain Tolerance:

For heat pain tolerance measurements, the thermode will be placed within the same surgically marked skin area of the anterior side of the right thigh, which was used to assess heat pain threshold. The thermode will have a baseline temperature of 32°C, and will be programmed

to gradually increase at a rate of 1.0°C per second. The subject will be given a controller in their dominant hand, to indicate when the heat-evoked pain has reached an intensity that is no longer tolerable, by pushing a button. At that time, the test will be stopped and the temperature returned to baseline within 1 second. This process will be repeated a further 2 times, with an interval of at least 1 minute between measurements (from start to start). The computer will record the average value of 3 experiments.

Safety Precautions

As there is a risk that OLP-1002 may affect the heat pain threshold, Covance CRU will put appropriate safety measures in place to ensure that subjects are not exposed to extremes of temperature when taking a shower or consuming hot drinks. During the heat pain safety assessments, the cut-off temperature for either test is 53°C in order to prevent skin injury.

7.3.6. Physical Examination

A full physical examination or symptom-directed physical examination will be performed at the timepoints specified in the Schedule of Assessments in [Appendix 6](#).

7.3.7. Body Weight and Height

Body weight (in underclothes) and height will be recorded at the times indicated in the Schedule of Assessments in [Appendix 6](#). BMI will be calculated using the following formula:

$$\text{BMI} = \frac{\text{body weight (kg)}}{(\text{height [m]})^2} \quad (\text{kg/m}^2)$$

7.3.8. Injection Site Assessments

Injection site assessments will be made at the times indicated in the Study Plan ([Appendix 6](#)).

Assessments will involve evaluation of the dosing site for the following criteria:

- Pain will be evaluated according to the following scale:

Grade 0	Grade 1	Grade 2	Grade 3	Grade 4
None	Does not interfere with activity	Interferes with activity or repeated use of non-narcotic pain reliever	Prevents daily activity or repeated use of narcotic pain reliever	Requires medical intervention greater than analgesia

- Redness will be assessed by estimating the size of the red patch at the injection site across its widest point, and will be evaluated according to the following scale:

Grade 0	Grade 1	Grade 2	Grade 3	Grade 4
0-24 mm	25-50 mm	51-100 mm	More than 100 mm	Requires medical intervention greater than analgesia

- Swelling will be assessed by estimating the size of the raised area around the injection site across its widest point, and will be evaluated according to the following scale:

Grade 0	Grade 1	Grade 2	Grade 3	Grade 4
0-24 mm	25-50 mm and does not interfere with activity	51-100 mm or interferes with activity	More than 100 mm and prevents daily activity	Requires medical intervention greater than analgesia

In addition, how the swelling affects the subject in their daily routing activities will be considered.

- Tenderness will be evaluated using the following scale:

Grade 0	Grade 1	Grade 2	Grade 3	Grade 4
None	Mild pain to touch	Moderate Pain to touch	Severe pain to touch	Requires medical intervention greater than analgesia

- Bruising and ulceration will be evaluated as being present or absent.

Local tolerability ratings of \geq Grade 3 and the presence of ulceration will be recorded as an adverse event.

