5.2. Study Treatment Administration

Subjects will be administered the IMP in numerical order. OLP-1002 will be administered by SC injection in the upper arm. If subcutaneous dosing of OLP-1002 in the upper arm is not possible, the subject may be dosed in the abdomen at the Investigator's discretion. For subjects in Groups A2, A4, A6, A9, A10, and A11, dosing will be on the opposite arm to the intradermal capsaicin test. At dose levels of ≥ 40 µg (Groups A9, A10, and A11), doses may be administered as multiple SC injections in the same location (ie, 2 SC injections in the upper arm).

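### The swelling scale in Section 7.3.8 switches from *or* at Grade 2 to *and* at Grade 3, so some swellings have no grade, some have two, and large or disabling swelling can miss automatic AE recording

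*Protocol*

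**What the plan says.** Section 7.3.8 grades swelling by its widest diameter together with its effect on activity:

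- Grade 0: 0-24 mm, with no activity condition.
- Grade 1: "25-50 mm and does not interfere with activity".
- Grade 2: "51-100 mm or interferes with activity".
- Grade 3: "More than 100 mm and prevents daily activity".
- Grade 4: "Requires medical intervention greater than analgesia".

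A sentence under the table adds: "In addition, how the swelling affects the subject in their daily routing activities will be considered". It does not say how this changes the grade.

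Two neighbouring scales are simpler. Redness over 100 mm is Grade 3 on size alone. Pain is Grade 3 when it "Prevents daily activity or repeated use of narcotic pain reliever", so preventing daily activity is enough by itself.

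The section ends with the recording rule. Local tolerability ratings at or above "Grade 3 and the presence of ulceration will be recorded as an adverse event". Section 2.2.1 lists injection site assessment, and the incidence and severity of AEs, among the primary safety endpoints.

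**The concern.** The connective changes from *and* (Grade 1) to *or* (Grade 2) and back to *and* (Grade 3). At Grade 2 either large size or interference is enough; at Grade 3 both conditions must hold. A swelling can therefore outgrow the Grade 2 size band without entering Grade 3. It can also prevent daily activity and stay at Grade 2 because it is not large enough. Since Grade 3 is the level that makes AE recording compulsory, the gap falls where the scale matters most. Part A groups have only 3 or 6 subjects on active drug, so one reaction left ungraded or graded low shows in a group summary. An analysis plan could not fully repair this, because the grade is assigned when the subject is assessed.

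**Working it through.** No sample size, power or error rate is involved. The check takes each of the four size bands against three levels of activity effect, 4 × 3 = 12 combinations, and lists every Grade 0-3 definition that each one meets. Grade 4 is left out because it depends on intervention, not on size or activity.

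**Reading 1: swelling that prevents activity also counts as interfering with it.**

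| Size | No interference | Interferes | Prevents |
|---|---|---|---|
| 0-24 mm | 0 | 0 and 2 | 0 and 2 |
| 25-50 mm | 1 | 2 | 2 |
| 51-100 mm | 2 | 2 | 2 |
| Over 100 mm | none | 2 | 2 and 3 |

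Eight combinations have exactly one grade, three have two, and one has none (8 + 3 + 1 = 12).

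**Reading 2: preventing is not counted as interfering.** Only the last column changes. It becomes 0, none, 2 and 3 from top to bottom. Nine combinations have one grade, one has two (0-24 mm, interferes), and two have none (9 + 1 + 2 = 12).

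Under both readings:

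- Over 100 mm with no interference has no grade. Redness of that size is Grade 3.
- Over 100 mm that interferes but does not prevent activity is Grade 2.
- No swelling of 100 mm or less that prevents daily activity rises above Grade 2. Pain that does so is Grade 3.
- Swelling of 0-24 mm that interferes meets Grades 0 and 2, and no rule says which to take.
- Only one combination, over 100 mm and preventing daily activity, reaches Grade 3.

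**Effect of changing only the connective.** With *or* at Grade 3 and no tie rule, no combination is ungraded, but under reading 1 six meet more than one definition: 0-24 mm interfering (0, 2); 0-24 mm preventing (0, 2, 3); 25-50 mm preventing (2, 3); 51-100 mm preventing (2, 3); over 100 mm interfering (2, 3); and over 100 mm preventing (2, 3). Adding a rule to assign the highest grade met leaves one grade per combination:

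| Size | No interference | Interferes | Prevents |
|---|---|---|---|
| 0-24 mm | 0 | 2 | 3 |
| 25-50 mm | 1 | 2 | 3 |
| 51-100 mm | 2 | 2 | 3 |
| Over 100 mm | 3 | 3 | 3 |

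This result is the same under both readings. Combinations at Grade 3 go from 1 to 6 of 12.

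**The case against.** The strongest reply is that the grade is not the only safeguard, and most of that stands.

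- Appendix 1 defines an AE broadly enough that any unfavourable sign after dosing can be recorded, whatever its local grade. Its definition of severe includes interruption of usual daily activities. Disabling swelling can therefore be recorded as a severe AE and, if at least possibly related, count toward the stopping criterion in Section 3.7.
- Swelling that needs intervention beyond analgesia is Grade 4 and falls under the recording rule.
- Under Section 3.6 the Investigator reviews all available blinded data, and the interim report covers all available safety assessments. Injection site findings reach the escalation decision without first becoming AEs. Section 3.7 also has a criterion for similar clinically relevant signs in two or more subjects, with no grade threshold.
- The sentence on daily activities shows that the effect of swelling is meant to be looked at. It assigns no grade, however, so two assessors following the text can still differ.

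Four stronger readings are tempting, and the documents do not support them. A reader might infer that serious swelling goes unreported or unseen at escalation; the routes above rule that out, and the point concerns large or disabling swelling, not SAEs in the Appendix 1 sense. A reader might infer that five of six important combinations are misgraded; those six are simply the ones the *or* rule sends to Grade 3, so the count is circular, and combinations are not event rates. A reader might infer that large swelling is likely in Groups A9 to A11, where "doses may be administered as multiple SC injections in the same location". At the supplied 100 µg/mL, 160 µg is 160 / 100 = 1.6 mL, but that is only the undiluted figure: Section 5.1 describes dilution, injected volumes are not stated, and nothing links volume to swelling over 100 mm. Finally, a one-word change looks sufficient, but the overlaps shown above remain without a tie rule.

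**Conclusion.** The swelling scale is inconsistent as written and should be corrected. Followed exactly, it leaves one combination of size and activity without a grade (two under the narrower reading of *interferes*) and gives three combinations two grades (one under the narrower reading). It also holds large or disabling swelling below the Grade 3 recording rule unless both conditions are met. The loss is of uniform, mandatory AE recording, not of every route to an AE or to the escalation review.

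The conclusion rests on a literal reading of the grade definitions. How often these combinations occur cannot be estimated from the protocol. The Amendment 6 summary in Appendix 7 reports single doses up to 20 µg as safe and well tolerated in Groups A1 to A8, so the practical effect may be small. The correction is still worthwhile because the scale feeds a primary safety endpoint and is cheap to repair.

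**What to change.** Reconcile the swelling definitions in Section 7.3.8 so that every combination of size and activity effect has exactly one grade. One form that does this, in line with the redness and pain scales, is to make Grade 3 swelling either more than 100 mm or preventing daily activity, and to state that the highest grade met is assigned. Make the same change on the assessment form, and have size and activity effect recorded separately.

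Section 7.3.8 does not say that both were captured for subjects already assessed. Regrade earlier records only where both are available, and leave the others as recorded.

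The cost is a small edit to the protocol and the form, and possibly a few more Grade 3 ratings and AE records.

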8. SAMPLE SIZE AND DATA ANALYSIS

8.1. Determination of Sample Size

No formal statistical assessment, in terms of sample size, has been conducted as this is the first time OLP-1002 is being administered to humans. However, the number of subjects in each part of the present study is common in early clinical pharmacology studies and is considered sufficient to achieve the objectives of the study. As part of Protocol Version 5, 3 additional groups will be included in Part A (Groups A9, A10, and A11) and 1 additional group will be included in Part B (Group B4). Up to 2 additional groups of 8 subjects may be added to Part B (6 active; 2 placebo).

8.2. Analysis Populations

8.2.1. Pharmacokinetic Population

The PK population will include all subjects who received at least 1 dose of OLP-1002 that have evaluable PK data and have had no AEs or protocol deviations considered to impact PK.

8.2.2. Pharmacodynamic Population

The PD population will include all subjects who received at least 1 dose of OLP-1002 or placebo and for whom PD can be evaluated.

8.2.3. Safety Population

The safety population will include all subjects who received at least 1 dose of OLP-1002 or placebo.

8.3. Pharmacokinetic Analyses

Noncompartmental PK analysis will be performed on individual plasma concentration data, using commercial software such as Phoenix[®] WinNonlin[®]. Plasma concentrations of OLP-1002 and PK parameters will be listed and summarized using descriptive statistics. Individual and arithmetic mean OLP-1002 concentration-time profiles will also be presented graphically.

8.4. Pharmacodynamic Analyses

Pharmacodynamic parameters will be listed and summarized using descriptive statistics. No formal statistical analysis of PD data is planned.

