2. OBJECTIVES AND ENDPOINTS

2.1. Objectives

The primary objective of the study is to assess the safety and tolerability of single and multiple SC doses of OLP-1002 in healthy subjects.

The exploratory objectives of the study are to evaluate the PD effect of OLP-1002 following single SC doses in healthy volunteers using a capsaicin pain model, and to monitor the effects of single SC doses of OLP-1002 on cardiac QT interval. Where possible, single and/or multiple subcutaneous dose pharmacokinetics of OLP-1002 in healthy subjects will be determined.

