3.1. Overall Study Design and Plan

3.1.1. Part A

Part A will comprise a single-dose, sequential-group design. Overall, 68 healthy subjects will be studied in 11 groups.

Potential subjects will be screened to assess their eligibility to enter the study within 28 days prior to the first dose administration. Potential subjects for Groups A2, A4, A6, A9, A10, and A11 will attend a pre-screening visit for an intradermal capsaicin test ([Section 3.4.2](#)).

Each subject will participate in 1 treatment period only, and will reside at the Clinical Research Unit (CRU) from Day -2 (2 days before dosing) to Day 3. All subjects will return for non-residential visits on Days 4, 7 (± 2 days), 10 (± 2 days), and 14 (± 2 days), and for a poststudy visit on Day 28 (± 2 days).

Based on the ongoing review of the safety and tolerability, additional non-residential visits may be required. The number of additional visits per subject will not exceed 3 and will not extend beyond Day 28 (± 2 days).

Doses will be administered in an escalating manner following satisfactory review of safety and tolerability data up to Day 10 (216 hours postdose) from the lower dose levels. For doses ≥ 12 μg , PK data will also be reviewed up to Day 7 prior to dose escalation.

[figure not shown]
In Part A, Groups A1, A3, A5, A7, and A8 will consist of 4 subjects; 3 subjects will receive OLP-1002 and 1 subject will receive placebo. To assess PD parameters, Groups A2, A4, A6,

A9, A10, and A11 will consist of 8 subjects; 6 subjects will receive OLP-1002 and 2 subjects will receive placebo.

Sentinel dosing will be employed for all groups in Part A. To maintain the blind in a 4-subject group, the first subject will be dosed 48 hours before the second subject, and the second subject will be dosed 48 hours prior to the third and fourth subjects. In PD assessment groups, 2 subjects (1 active: 1 placebo) will be dosed 48 hours before the remaining 6 subjects (5 active: 1 placebo).

An overview of the study design is shown in [Figure 1](#).

Figure 1: Study Schematic (Part A)

Active = OLP-1002; SC = subcutaneous.
Six groups consist of 8 subjects (6 active: 2 placebo); all other groups will consist of 4 subjects (3 active: 1 placebo).

The total duration of study participation for each subject (from Screening through Follow-up visit) is anticipated to be approximately 8 weeks.

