6. CONCOMITANT THERAPIES AND OTHER RESTRICTIONS

6.1. Concomitant Therapies

Subjects will refrain from use of any prescription medications/products from 14 days prior to dosing until the Follow-up visit, and non-prescription medications/products from 7 days prior to dosing until the Follow-up visit, unless the Investigator (or designee) and/or Sponsor have given their prior consent.

Paracetamol/acetaminophen (2 g/day for up to 3 consecutive days), hormone-replacement therapy, oral, implantable, transdermal, injectable, or intrauterine contraceptives are acceptable concomitant medications. The administration of any other concomitant medications during the study is prohibited without prior approval of the Investigator (or designee), unless its use is deemed necessary for treatment of an AE. Any medication taken by a subject during the course of the study and the reason for its use will be documented in the source data.

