7.2. Pharmacodynamic Assessments

Capsaicin intradermal test will be performed for subjects in Groups A2, A4, A6, A9, A10, and A11. Each subject will be tested at a pre-screening visit before being tested twice during the study (1 predose and 1 postdose).

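### The PD analysis is fixed as descriptive only, so no active-versus-placebo difference with an interval is planned, although the baseline and 12 placebo subjects needed for a usable estimate are already in the design

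*Protocol*

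**What the plan says.** Section 8.4 of the protocol (Version 5) states the PD method in two sentences: "Pharmacodynamic parameters will be listed and summarized using descriptive statistics", and then "No formal statistical analysis of PD data is planned". The statistical methods part of the synopsis repeats both.

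The design around that choice is as follows.

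- Section 2.1 makes PD an exploratory objective: "The exploratory objectives of the study are to evaluate the PD effect of OLP-1002 following single SC doses in healthy volunteers".
- Section 3.1.1 gives the size, "Overall, 68 healthy subjects will be studied in 11 groups", and the allocation, "Six groups consist of 8 subjects (6 active: 2 placebo); all other groups will consist of 4 subjects (3 active: 1 placebo"). The PD groups are A2, A4, A6, A9, A10 and A11.
- Section 3.4 takes groups of 4 to be enough for safety and tolerability, and gives assessment of PD as the reason for six groups of 8. It also says placebo was chosen so that treatment effects can be told apart from the effects of study conditions.
- Section 7.2 provides a baseline for each PD subject: "Each subject will be tested at a pre-screening visit before being tested twice during the study (1 predose and 1 postdose").
- Section 1.6 expects the PD data to help set doses and regimens for later patient studies.
- Section 8.2.2 includes placebo subjects in the PD population. Section 8.1 reports no formal sample size calculation.

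**The concern.** The exclusion of formal PD analysis is a stated decision in two places, so it is not a detail left open for the SAP. An SAP that added a modelled contrast would depart from the protocol.

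The decision sits awkwardly with the rest of the design. Raising six groups from 4 to 8 accounts for 6 x 4 = 24 of the 68 Part A subjects. PD subjects have three capsaicin tests, and Section 1.7 acknowledges the extra discomfort. Concurrent placebo is there to separate drug effect from study conditions. A table of 6 active values beside 2 placebo values, with no estimated difference and no interval, gives the reader little means of doing that. Section 3.4.2 accepts VAS responders from 3 to 9, so between-subject spread may be wide and a chance difference could be read as analgesia, or a real one missed. The figures may then guide later dose choice.

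**Working it through.** **Inputs.** Group counts and allocation come from Section 3.1.1. The protocol gives no SD and no baseline-to-postdose correlation for the capsaicin endpoints: Section 3.4.2 cites a validation study without figures. Results are therefore in units of the endpoint SD, and correlations of 0, 0.5 and 0.7 are assumed.

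**The protocol's own count.** 5 x 4 + 6 x 8 = 68, as stated. PD groups: 6 x 6 = 36 active and 6 x 2 = 12 placebo, 48 in all.

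**Formula.** Half-width = t(0.975, df) x SD x sqrt(1/n_active + 1/n_placebo). For ANCOVA, multiply by sqrt(1 - r^2), where r is the baseline correlation. This ignores chance baseline imbalance and assumes a common slope.

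**One dose group against its own 2 placebo subjects.** SE = sqrt(1/6 + 1/2) = 0.816 SD.

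- Group analysed alone, 8 - 2 = 6 df: 2.447 x 0.816 = 2.00 SD.
- Variance pooled over all 12 group-by-treatment cells, 48 - 12 = 36 df: 2.028 x 0.816 = 1.66 SD.

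**The same dose group against 12 pooled placebo subjects.** SE = sqrt(1/6 + 1/12) = 0.500 SD. The model has seven arms (six doses and placebo).

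- No covariate, 48 - 7 = 41 df: 2.020 x 0.500 = 1.01 SD.
- With baseline covariate, 40 df, t = 2.021:
  - r = 0: 1.01 SD
  - r = 0.5: 1.01 x 0.866 = 0.88 SD
  - r = 0.7: 1.01 x 0.714 = 0.72 SD

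**Where the gain comes from.** Going from 2.00 to 1.66 SD is better estimation of the variance. Going from 1.66 to 1.01 SD is the extra placebo subjects: 1.01/1.66 = 0.61, the same as the SE ratio 0.500/0.816 = 0.61. Placebo pooling by itself is therefore worth a 39% reduction.

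**Cost of separating early and late groups.** A2/A4/A6 and A9 to A11 each contain 24 subjects, with 6 placebo. SE = sqrt(1/6 + 1/6) = 0.577 SD. With three doses, placebo and a covariate, df = 24 - 5 = 19, and the half-width at r = 0 is 2.093 x 0.577 = 1.21 SD.

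**Number of intervals.** Pain AUC, Emax and hyperalgesia area at 5 and at 30 minutes make 4 endpoints. Over 6 doses that is 24 intervals, of which 24 x 0.05 = 1.2 would be expected to exclude zero by chance if there were no effect.

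**The case against.** The strongest reply is that nothing here is wrong. PD is exploratory in a first-in-human safety study with no formal sample size, and the protocol promises no PD effect size. Descriptive analysis is a common choice in that setting, and preferring ANCOVA is to some extent taste. This stands as far as it goes: the point is an improvement, not a correction. It does not remove the mismatch between a placebo-controlled PD component and a plan with no estimated contrast.

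A second reply concerns pooling, and it also stands in part. Amendment 6 (Appendix 7) added A9 to A11 when A1 to A8 had already been dosed, and Section 5.2 lets their doses be given as more than one injection. Pooling placebo assumes that neither difference matters, and splitting the groups to check this widens the interval again, to about 1.21 SD.

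A reader might also infer several stronger things that the documents do not support.

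- *That the plan throws away the baseline, or rules out any drug-placebo estimate.* Section 8.4 excludes formal analysis. It does not forbid change-from-baseline summaries or pooled placebo summaries, and such details are commonly left to the SAP.
- *That A9 to A11 were added to test analgesia.* Appendix 7 says they were added to raise the maximum dose. PD explains why they have 8 subjects.
- *That the interval would be 2.0 to 2.8 times narrower.* That takes the 6-df comparison as the baseline, which the protocol does not specify, and at its upper end also takes an assumed correlation of 0.7.
- *That permitted paracetamol (Section 6.1) biases the PD comparison and calls for an exclusion rule.* The in-study PD tests in Part A fall within residency, and Section 8.2.2 already requires that PD can be evaluated. The direction of any bias is unknown, and excluding subjects on postdose medication use could itself bias groups of 6 and 2.

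**Conclusion.** The point holds as a worthwhile, low-cost improvement. The protocol commits itself to descriptive PD analysis and so plans no active-versus-placebo contrast with an interval, while already collecting what a useful exploratory estimate needs.

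A dose group judged against its own 2 placebo subjects is known only to about plus or minus 2.00 SD, or 1.66 SD with pooled variance. Against 12 pooled placebo subjects it is about 1.01 SD. The like-for-like gain from pooling is 39%. Anything beyond that depends on the baseline correlation, which the protocol does not give. The figures also assume a common variance and no cohort or time effect among placebo subjects. Even at 1.01 SD the estimates remain imprecise, which is a reason to report intervals and to make no efficacy claim.

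**What to change.** Replace the sentence excluding formal PD analysis, in Section 8.4 and in the synopsis, with an exploratory, estimation-only analysis:

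- ANCOVA for capsaicin pain AUC, Emax, and area of secondary hyperalgesia at 5 and at 30 minutes.
- Each dose group compared with pooled placebo, with the predose value of the same measure as covariate.
- Differences reported with 95% confidence intervals and no hypothesis claims, with a statement that the intervals are not adjusted for multiplicity.
- A sensitivity analysis that separates A2/A4/A6 from A9 to A11, each with its own 6 placebo subjects.

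Heat-pain threshold and tolerance should not be put into this model. They are measured in all 68 Part A subjects at several postdose times and would need a model of their own; otherwise they can stay descriptive.

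The cost is a little programming and reporting, with no extra subjects, tests or visits. The downside is the reliance on no cohort or time effect, and the sensitivity split that checks it gives back part of the precision gained.
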